7 DATA HANDLING METHODS

For details of the data handling methods, refer to Statistical Analysis Plan v3.0, dated 14 February 2019.

Missing data for adherence to ferric maltol (i.e. no returned bottles and no pill count) will not be imputed and will not be assumed to be zero adherence or all tablets taken.

The code for implementing the SAS® procedure MI is:

```
PROC MI DATA = <dataset _name> NIMPUTE = 20 SEED = <seed> OUT = MI_out;  
  VAR baselineHbtrans gender ibd Week4Hbtrans Week12Hbtrans;  
  EM MAXITER = 10000;  
RUN;
```

For the multiple imputation, the code for implementing the SAS® procedure MIANALYZE to the CFB Hb concentration at Week 12 secondary endpoint is:

```
DATA CFB_Impute; SET MI_out; CFBHbW12 = Week12Hb - baselineHb; RUN;  
  
PROC SORT DATA = CFB_Impute; BY _Imputation_; RUN;  
  
PROC REG DATA = CFB_Impute OUTEST = outreg COVOUT;  
  BY _Imputation_;  
  MODEL CFBHbW12 = binarybaselineHb TreatmentArm IBDGroup;  
RUN;  
  
PROC MIANALYZE DATA = outreg EDF = <complete-data degrees of freedom>;  
  MODELEFFECTS Intercept binarybaselineHb TreatmentArm IBDGroup;  
  ODS OUTPUT ParameterEstimates = parm1;  
RUN;
```

The code for implementing the SAS® procedure MIANALYZE to the Hb normal limit responder at Week 12 secondary endpoint for the ITT population is:

```
DATA NormalHb_Impute; SET MI_out;  
  NLResponder = 0;  
  IF Gender = 'F' AND Week12Hb => 12.0 THEN NLResponder = 1;  
  IF Gender = 'M' AND Week12Hb => 13.0 THEN NLResponder = 1;  
RUN;  
  
PROC SORT DATA = NormalHb_Impute; BY _Imputation_; RUN;  
  
PROC LOGISTIC DATA = NormalHb_Impute;  
  MODEL NLResponder = binarybaselineHb TreatmentArm IBDGroup / covb;  
  BY _Imputation_;  
  ODS OUTPUT ParameterEstimates = lgsparms  
               CovB              = lgscovb;  
RUN;  
  
PROC MIANALYZE PARMS = lgsparms COVB(effectvar=stacking) = lgscovb;  
  MODELEFFECTS Intercept binarybaselineHb TreatmentArm IBDGroup;  
RUN
```

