4 POWER AND SAMPLE SIZE CONSIDERATIONS

This study is designed with a 'responder %' primary endpoint, where responder is a subject who either has at least 2g/dL rise in Hb from baseline or has shift from baseline of anaemic to non-anaemic status. The primary endpoint is the Hb responder rate at Week 12. The comparator group (IV Iron) responder rate is assumed to be 75% and the absolute non-inferiority margin is 20%. The non-inferiority margin is based on clinical opinion, coupled with the fact that in a previous study, the response rate in the placebo arm was less than 5% at 12 weeks.

The study is powered at 90% when the true response rate in the ferric maltol arm is 75% (i.e., the true difference in response rate to IV Iron is 0%). The primary statistical test is based on the 2-sided 95% confidence interval for the difference in response rates between the two treatment groups. This requires 108 subjects per treatment arm. In order to allow for protocol deviations, the sample size has been increased by 12% to 121 subjects per treatment arm.

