7.1.2 Non-Date Values

Every effort will be made to obtain required data at each scheduled evaluation from all subjects who have been enrolled. Missing values for the primary efficacy endpoint of Hb responder (i.e., a subject who either has at least 2g/dL rise in Hb from baseline or has shift from baseline of anaemic to non-anaemic status) at Week 12 will be imputed using a Multiple imputation approach for the primary efficacy analysis on the ITT population. If the value of Hb is missing, multiple imputation based on pre-treatment visits will be used in the baseline and multiple imputation based on post-treatment visits will be used to determine the post-baseline value to be used in the primary efficacy endpoint analysis on the ITT population.

As additional sensitivity analyses, missing values for the primary efficacy endpoint on the ITT population will also be imputed using a Last Observation Carried Forward (LOCF) approach up to Week 12.

Missing values for efficacy variables will be replaced for the secondary endpoint analyses, as follows:

- For the key endpoint, 'Hb concentration within normal limits', subjects not returning to a follow-up visit will be assumed to have Hb concentration not within normal limits.
- For the endpoint, 'Increases in Hb concentration of $\geq 1\text{g/dL}$ ', subjects not returning to a follow-up visit will have their Hb concentration imputed using multiple imputation.
- For the endpoint, 'Increases in Hb concentration of $\geq 2\text{g/dL}$ ', subjects not returning to a follow-up visit will have their Hb concentration imputed using multiple imputation.

Missing values for the long-term secondary efficacy endpoints, normalization of Hb at 6 and 12 months and normalization of ferritin at 6 and 12 months, will not be imputed.

Missing values for the SF-36 pharmacoeconomic analysis will be imputed by a LOCF approach up to Week 12. Missing values for all other pharmacoeconomic analyses will be kept as missing.

Safety data will be used according to availability, with no imputation for missing data.

Imputation of data values will only be carried out, where indicated, for computational purposes and fitting of models. Actual data values, as they appear in the original CRFs, will be shown in the data listings.

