Note that missing values for the Hb responder status at Week 12 primary efficacy analysis will be imputed using a multiple imputation approach for ITT population. BOCF will be used in the case of missing baseline data to use the screening value. Missing values of Hb concentration at Week 12 will be imputed using the SAS[®] procedure MI. This will generate 20 complete datasets containing imputed values of Hb concentration at Week 12 for those missing in the original dataset. Variables considered helpful in guiding this imputation are baseline (Visit 2) Hb concentration and treatment arm. The code for implementing the SAS[®] procedure MI is:

```
PROC MI DATA = <dataset _name> NIMPUTE = 20 SEED = <seed> OUT = MI_out;  
  VAR baselineHb TreatmentArm Week12Hb;  
  EM MAXITER = 10000;  
RUN;
```

Each model, corresponding to a given endpoint analysis, will be fitted against each of the imputed datasets. The SAS[®] procedure MIANALYZE will then be used to combine the individual analysis results for the given endpoint into one result.

The null hypothesis for the primary efficacy analysis will be rejected (i.e., ferric maltol will be deemed non-inferior to IV Iron), if the LCL of the 95% CI for the difference (ferric maltol - IV Iron) in proportions of Hb responders at Week 12 (BOCF) is $\geq -20\%$ for both the ITT analysis and the PP analysis. The p-value in testing the aforementioned hypotheses will be equal to one minus the confidence coefficient corresponding to the CI for the risk difference whose LCL equals -20% (i.e., inverting the CI for the risk difference to a test statistic and calculating the p-value from the test statistic).

The proportion of Hb responders will be summarised for the ITT and PP populations using descriptive statistics by visit over the Treatment Period for each treatment

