The proportion of Hb responders at Week 12 will be compared between the two treatment arms, by calculating a 2-sided confidence interval for difference in the proportions of Hb responders (risk difference) between the two treatment arms and comparing the lower confidence limit of this CI to the pre-specified non-inferiority margin. The CI will be calculated using the Delta Method approach [1] based on a logistic regression model, adjusted for treatment arm, baseline Hb (below the observed median or at least the observed median), and IBD subgroup (UC or CD). Note: For the CI calculation in the primary efficacy endpoint, the risk difference model was applied in the original analysis for CSR v1.0. The analysis method will be corrected to the Delta Method approach in the current post hoc analysis.

Post-hoc change: Note that missing values for the Hb responder status at Week 12 primary efficacy analysis will be imputed using a multiple imputation (MI) approach for ITT population. Missing values of Hb concentration at Week 12 will be imputed using the SAS[®] procedure MI. This will generate 20 complete datasets containing imputed values of Hb concentration at Week 12 for those missing in the original dataset. Variables considered helpful in guiding this imputation are deviation of baseline (Visit 2) Hb concentration from response threshold, deviation of Week 4 Hb concentration from response threshold, gender and IBD subgroup. A separate model will be computed for each treatment arm.

The Week 12 imputed value will then be back transformed from the Week 12 deviation from the response threshold.

Each model, corresponding to a given endpoint analysis, will be fitted against each of the imputed datasets. The SAS[®] procedure MIANALYZE will then be used to combine the individual analysis results for the given endpoint into one result.

The null hypothesis for the primary efficacy analysis will be rejected (i.e., ferric maltol will be deemed non-inferior to IV Iron), if the LCL of the 95% CI for the

difference (ferric maltol – IV Iron) in proportions of Hb responders at Week 12 is $\geq -20\%$ for both the ITT analysis and the re-evaluated PP analysis. The p-value in testing the aforementioned hypotheses will be equal to one minus the confidence coefficient corresponding to the CI for the risk difference whose LCL equals -20% (i.e., inverting the CI for the risk difference to a test statistic and calculating the p-value from the test statistic).

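### The post hoc PROC MI code omits treatment arm and the back-transform, contradicting the text's separate model per arm; run as printed, it gives an arm-blind imputation for the primary ITT analysis

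*SAP*

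**What the plan says.** The document holds two plans: SAP v3.0 and a later post hoc SAP that revises it.

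- **Post hoc SAP, Section 9.1.1 (text).** The predictors are baseline and Week 4 Hb, each as a deviation from the response threshold, plus gender and IBD subgroup. Then: "A separate model will be computed for each treatment arm". And: "The Week 12 imputed value will then be back transformed from the Week 12 deviation from the response threshold".
- **Post hoc SAP, Section 7 (code).** One call, "PROC MI DATA = <dataset _name> NIMPUTE = 20 SEED = <seed> OUT = MI_out", with "VAR baselineHbtrans gender ibd Week4Hbtrans Week12Hbtrans". The next steps read `MI_out`, compute change from baseline and normal-limit status from `Week12Hb`, and fit `TreatmentArm` as a covariate.
- **SAP v3.0, Section 9.1.1 (code).** "VAR baselineHb TreatmentArm Week12Hb". Treatment arm was in the list.
- **Success rule (post hoc SAP, Section 9.1.1).** The lower limit of the 95% CI must be at or above -20% in both the ITT and the re-evaluated per-protocol (PP) analyses. SAP v3.0, Section 5.4 excludes from PP subjects who do not attend Week 12 and have no Week 12 Hb.

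**The concern.** The post hoc revision removed arm from the variable list but did not print the BY statement that would replace it. A programmer who follows Section 7 and one who follows Section 9.1.1 obtain different primary ITT results.

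An imputation model without arm draws missing Week 12 values from a mixture of both arms, apart from what Week 4 Hb says about arm. That usually pulls the arms together. In a superiority trial such dilution costs power. In a non-inferiority trial it can hide a true deficit, and the ITT lower limit is one of the two conditions for declaring success.

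The second gap is silent. If `Week12Hb` is never rebuilt from the imputed `Week12Hbtrans`, output labelled MI contains no imputation, and no error appears.

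**Working it through.** **1. The plan's own figures.** SAP v3.0, Section 4 gives 75% response in both arms, a margin of 20 points, 90% power and a two-sided 95% CI.

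- n0 = [0.75×0.25 + 0.75×0.25] × (1.960 + 1.282)² / 0.20² = 98.5 per arm.
- With continuity correction: (n0/4) × [1 + √(1 + 4/(0.20 n0))]² = 108.3, which reproduces the stated 108.
- 108 × 1.12 = 120.96, which reproduces 121.

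These figures do not depend on the imputation. They fix the setting below: 121 per arm, with a true 75% against 55% at the margin.

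**2. Does the code pool the arms?** The input dataset name is a placeholder, so one run per arm is conceivable. But the output name is fixed. Two runs as printed would overwrite the first, and no append step is given. Later steps need both arms in `MI_out`. Elsewhere in Section 7, `BY _Imputation_` is written out where it is needed. As printed, this is one run on both arms.

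**3. Upper bound on the dilution.** Suppose the imputed values carry no arm information, a share m is missing in each arm, and the complete-data standard error applies. The expected difference is then (1 − m) × (−20).

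- SE = √[(0.75×0.25 + 0.55×0.45)/121] = 0.0600.
- m = 12%: −17.6 points; P(lower limit ≥ −20%) = Φ(0.024/0.0600 − 1.96) = 5.9%.
- m = 20%: −16.0 points; Φ(0.040/0.0600 − 1.96) = 9.8%.

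This is a worst case, because Week 4 Hb is in the model and multiple imputation widens the variance.

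**4. Simulation at a true difference of −20.** It used 1,500 trials per setting, 20 imputations, the post hoc variable list, a logistic delta-method risk difference and Rubin's rules. The documents give no missing rate, SD or visit correlation. Assumed: SD 1.0 at Week 4 and 1.4 at Week 12, correlation 0.65. The Monte Carlo SE of a 2.5% rate is √(0.025×0.975/1500), or 0.4 points. Each cell shows the estimated difference and the chance of ITT success.

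| Week 4 gap ÷ Week 12 gap | Missing Week 12 | Of those, Week 4 also missing | Pooled | Per arm |
|---|---|---|---|---|
| 0.5 | 12% | half | −18.2; 2.7% | −20.0; 1.7% |
| 1.0 | 12% | half | −18.8; 2.3% | −20.0; 1.7% |
| 1.5 | 12% | half | −19.2; 1.9% | −20.0; 1.7% |
| 0.5 | 20% | half | −16.7; 3.3% | −19.8; 1.1% |
| 1.0 | 20% | half | −17.6; 2.3% | −19.7; 1.1% |
| 1.5 | 20% | half | −18.3; 1.5% | −19.7; 1.1% |
| 0.5 | 20% | none | −17.9; 3.4% | −20.0; 1.7% |
| 1.0 | 20% | none | −19.7; 1.2% | −20.0; 1.7% |
| 1.5 | 20% | none | −21.2; 0.7% | −20.0; 1.7% |

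With truly equal arms and 12% missing (400 trials per setting), the pooled estimate was −0.1 to −0.4 points.

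**5. Back-transform.** PROC MI fills `Week12Hbtrans`. `Week12Hb` stays missing for exactly the subjects being imputed. `CFBHbW12` is then missing, PROC REG drops those rows, and the MI ANCOVA becomes a complete-case analysis.

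The inverse cannot be written from the plan as it stands, because the response threshold is not defined. Response is a rise of at least 2 g/dL or normalization. For a woman with baseline 8 g/dL, the rise route gives 8 + 2 = 10 g/dL and the normalization route 12 g/dL. A wrong choice would misplace her imputed value by 2 g/dL.

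**The case against.** The strongest defence is that the snippet is a template and the text states the method outright. Dropping arm from the list is what a per-arm run requires, and the listed predictors match the text. That stands as evidence of intent. It does not make the printed code carry out that intent, for the reasons in step 2 of the working.

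A reader might infer that the non-inferiority test is biased toward success. The documents do not support that in general:

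- The direction depends on a true deficit and on how Week 4 Hb tracks Week 12 Hb. It vanishes with equal arms, which is the design assumption, and reversed in one setting.
- Several pooled false-success rates lie below the nominal 2.5%, because Rubin's variance is wide here.
- Success also needs PP, which this imputation does not touch. The chance of meeting both conditions cannot exceed the smaller of the two.
- An ITT observed-cases analysis is planned (post hoc SAP, Section 9.1.2.1).

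Three further inferences fail:

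- Missing Week 12 Hb giving `NLResponder` = 0 is not in itself an error. Post hoc Section 9.2.1.1 prescribes it, although the same section labels the endpoint MI.
- Not every MI endpoint is affected. Week 12 serum ferritin is analysed with MI, but ferritin is not in this model.
- The v3.0 model is not contradicted by its own Section 9.1.1, where text and code agree. Only the absence of Week 4 Hb sits awkwardly with v3.0 Section 7.1.2 ("multiple imputation based on post-treatment visits will be used to determine the post-baseline value"), and the post hoc text replaces that model.

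**Conclusion.** The contradiction between text and code is certain, and it affects the primary ITT analysis. As printed, the code imputes Hb without regard to arm and never returns the imputed value to the variable analysed.

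The size is conditional. At a true difference of −20 points, with 12-20% missing and half of those also lacking Week 4 Hb, the ITT deficit shrinks by 0.8 to 3.3 points, and ITT false success is 1.5-3.3% against 1.1-1.7% with per-arm models. These figures rest on the assumed missing rates, SDs and correlation. They are ITT rates, not the error rate of the trial's two-part decision. The documents do not show which model was actually run, so it cannot be said that any reported result is wrong. The correction should be made because the primary analysis must be reproducible from its specification.

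**What to change.** 1. Sort by arm and add `BY TreatmentArm;` to the PROC MI step, keeping the variable list. `MI_out` then holds both arms.
2. Define the response threshold used in the forward transform. Code its exact inverse to obtain `Week12Hb` before the change-from-baseline and Hb responder steps.
3. Reconcile the MI label on the Hb normal-limit responder endpoint with the rule that missing Week 12 Hb counts as non-response.
4. Give serum ferritin its own imputation model.
5. Confirm which model produced the reported Hb results, and rerun the ITT analyses if it was pooled or if the back-transform was missing.

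The cost is a few lines of code and, if needed, a rerun. Per-arm models may lose a little power: with equal arms and 12% missing, the simulated chance of ITT success was 94.8% and 92.5% (missingness split evenly and unevenly between arms), against 95.5% and 95.3% pooled. With 400 trials per setting, each rate has a Monte Carlo SE of about 1.1 points. Both per-arm rates stay above the planned 90%.

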8 STUDY POPULATION

For details of the listings and summaries for the study population, refer to Statistical Analysis Plan v3.0, dated 14 February 2019.

In addition to the existing categories described in Statistical Analysis Plan v3.0, dated 14 February 2019, additional major protocol deviations include the following categories:

- Repeated non-compliance in self-administration of ferric maltol study drug, where non-compliance is less than 80% or greater than 120% of expected administration of study drug in the first 12 weeks. Where data were missing the compliance may be assessed based on individual visit pill returns, where data exists the compliance would be based on the average compliance in the first 12 weeks of study.
- Subjects that had a Week 12 haemoglobin value measured more than 2 weeks (+/- 14 days) outside the planned Week 12 assessment, ie an additional 1 week window beyond the 1 week window in the schedule of assessments.
- IV Iron subjects who did not follow the specific country dosing regimens. An IV iron dose up to Week 12 that was ≥ 2 or $\leq .5$ times the calculated dose based on weight and Hb and per the local Prescribing Information, will not be included in the re-evaluated PP population.
- Immunosuppressant use will not be a criterion for exclusion from the re-evaluated PP population, based on protocol version 6, dated 11 July 2017.

Protocol deviations deemed to be major, but not recorded on the database, will be included by means of a spreadsheet which will be agreed by Shield and Clinipace based on the minutes of the subject evaluability meeting.

No imputation was performed for missing data in compliance calculations.

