5.4 Per Protocol (PP) Population

The PP population will consist of those randomized subjects who do not have major protocol deviations during the first 12 weeks of the study. Protocol deviations occurring during the study will be classified as major or minor prior to database lock. See [Section 8.4](#) for definitions of protocol deviations. In addition, patients who do not attend week 12 and have no Hb result at week 12 will be excluded from the PP population.

The ITT and PP population will be used in the primary efficacy analysis. Tables summarised or analysed using the ITT population will be presented by randomized treatment. Tables summarised or analysed using the PP population will be presented by actual treatment given.

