8.4 Protocol Deviations

Major deviations, for the purpose of the statistical analyses, are defined to be those deviations that could potentially bias either efficacy or safety conclusions of the study. Subjects associated with major protocol deviations will be identified and flagged prior to freezing (or, locking) the database at each of the two planned database freeze (or, lock) timepoints (interim analysis freeze/lock and end-of-study freeze/lock).

Major protocol deviations include, but are not limited to, the following categories:

- Subjects that received at least one dose of a study drug and who did not satisfy major inclusion/exclusion criteria.
- Subjects meeting conditions for withdrawal who were not withdrawn.
- Subjects that received a prohibited concomitant medication.
- Subjects that had at least one major required protocol procedure not being performed. Examples of major required protocol procedures include missing haemoglobin results at baseline and/or at Week 12.
- Subjects that received the opposite study drug treatment than the one to which they were randomized.
- Repeated non-compliance in self-administration of ferric maltol study drug, where non-compliance is less than 80% or greater than 120% of expected administration of study drug.
- Other relevant deviations, to be judged on an individual basis.

Protocol deviations will be summarised with frequency distributions (counts and percentages) by treatment arm, category, and deviation type (minor and major) for the ITT population. The denominators for calculating percentages will be based on the number of subjects in the analysis population for each treatment arm and overall.

Protocol deviations will be provided within a data listing by subject.

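### Off-database major deviations can enter the re-evaluated Per Protocol set through a spreadsheet agreed after CSR v1.0, and no planned output shows how far the PP lower limit depends on them

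*SAP*

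**What the plan says.** The file holds SAP v3.0 and, after it, a post hoc addendum whose results go into version 2 of the CSR.

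- **SAP v3.0, section 5.4:** "Protocol deviations occurring during the study will be classified as major or minor prior to database lock". Section 8.4 likewise has major deviations flagged before the database is frozen or locked.
- **SAP v3.0, section 8.4:** a major deviation is one that could bias the efficacy or safety conclusions. The list of categories is expressly not exhaustive and ends with "Other relevant deviations, to be judged on an individual basis".
- **Addendum, section 8:** the v3.0 categories are kept and new ones added. Then: "Protocol deviations deemed to be major, but not recorded on the database, will be included by means of a spreadsheet which will be agreed". The two companies named there are to agree it from the minutes of the subject evaluability meeting. Section 12 repeats this among the post hoc changes.
- **Addendum, section 9.1.1:** ferric maltol is deemed non-inferior if the lower 95% limit is at least -20% "for both the ITT analysis and the re-evaluated PP analysis".
- **SAP v3.0, section 3.1:** the trial is open-label.
- **Addendum, sections 5 and 9.1.1:** both refer to the analysis already done for CSR v1.0.

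**The concern.** Under v3.0, case-by-case judgement was tied to a step completed before lock. The addendum uses the same open category after the first analysis has been reported, and on evidence that is not in the database. It gives no date for the evaluability meeting, does not say whether its members could see arm or Hb response, and puts agreement of the spreadsheet in the future. Someone deciding whether a subject belongs in the PP set may therefore already know how that subject counts.

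The PP analysis is one of two required conditions, so its membership matters. The added sensitivity sets do not isolate the effect. The two modified PP sets restore only subjects excluded solely for compliance or solely for Week 12 windowing, and the protocol-version analysis stays inside the re-evaluated PP set. Comparison with CSR v1.0 does not help either, because the visit window, the IV dosing rule, the immunosuppressant rule, the Hb threshold for normalisation (in v3.0) and the interval method also differ.

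**Working it through.** **Inputs from SAP v3.0, section 4.** Responder rate 75% in both arms, margin 20 points, 90% power. On the test: "The primary statistical test is based on the 2-sided 95% confidence interval for the difference in response rates between the two treatment groups". On the size: "This requires 108 subjects per treatment arm", raised by 12% to 121.

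**The plan's own figure.** Unpooled formula: n = 2 × 0.75 × 0.25 × (1.960 + 1.282)² / 0.20² = 98.5. With the continuity correction, (n/4) × [1 + √(1 + 4/(0.20n))]² = 108.3, which reproduces 108. Then 108 × 1.12 = 120.96, i.e. 121. The allowance for deviations is 121 - 108 = 13 per arm.

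**Fragility of the PP limit.** The documents give no results, so these are assumptions: 108 per arm in PP, 81/108 (75%) responders on IV iron, and an unadjusted Wald interval in place of the adjusted delta-method one. The lower limit is

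(p₁ - p₂) - 1.960 × √[p₁(1 - p₁)/n₁ + p₂(1 - p₂)/n₂].

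For 72/108: -8.33 - 1.960 × 6.16 = -20.41. Removing one non-responder (72/107): -7.71 - 1.960 × 6.16 = -19.78.

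| Ferric maltol before | Lower limit | Removed | Lower limit after |
|---|---|---|---|
| 72/108 | -20.41 (fails) | 1 non-responder | -19.78 (passes) |
| 70/108 | -22.34 (fails) | 4 non-responders | -19.86 (passes) |
| 68/108 | -24.27 (fails) | 7 non-responders | -19.94 (passes) |
| 73/108 | -19.43 (passes) | 2 responders | -20.14 (fails) |
| 81/108 | -11.55 (passes) | 24 responders needed to fail | |

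Each non-responder removed moves the limit by about 0.6 to 0.7 points. The counts of 1 to 7 lie within the allowance of 13. With equal rates, no plausible number of exclusions changes the result.

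**Error of the whole rule.** I simulated 1,000,000 trials at a true difference of -20 points (55% against 75%), with a PP set of 108 per arm nested in an ITT set of 121 and every exclusion a ferric maltol non-responder.

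| Selective exclusions | PP passes | ITT and PP both pass |
|---|---|---|
| 0 | 2.4% | 1.6% |
| 3 | 4.4% | 2.1% |
| 5 | 6.5% | 2.3% |
| 7 | 9.2% | 2.4% |

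ITT alone passes in 2.4%. The joint rate cannot exceed that however many subjects leave the PP set.

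**The case against.** Five points can be made for the plan.

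- **ITT protects the claim.** ITT comprises all randomised subjects, and the spreadsheet does not change it. A reader might infer from the PP column that the trial's false-claim rate rises to 6.5% or more. It does not, because both analyses must pass. In the 68/108 example, carrying similar rates to 121 per arm (76/121 against 91/121, an assumption) gives an ITT limit of -23.9, so the claim would fail whatever happened in PP. This stands, and it limits the size of the concern.
- **The work is labelled post hoc.** SAP v3.0 section 6.1 calls analyses designed after lock exploratory, and addendum section 6 requires labelling. This stands as disclosure. Addendum section 9.1.1 nevertheless keeps the formal rule and applies it to the re-evaluated PP set.
- **The spreadsheet has a source.** It must follow meeting minutes, and section 8.4 says what major means. It is therefore too strong to say that nothing limits the entries. But the definition is broad, the list is open, and the minutes are undated.
- **The decisions may predate lock.** A reader might infer that exclusions were made with results in hand. The documents do not say so: the minutes could record pre-lock decisions, and only agreement of the spreadsheet is placed in the future. They show an opportunity and no more.
- **Exclusions are traceable.** SAP v3.0 section 8.1 plans a listing with the reason for each exclusion, and addendum section 14.3 reissues the listings of deviations and analysis populations. These show who was excluded, but not the effect on the lower limit.

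The direction is also not fixed: exclusions can hurt ferric maltol as well as help it.

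**Conclusion.** The point holds in a limited form. The addendum moves part of the PP classification from before lock to after CSR v1.0, in an open-label trial, with an open category still available and no analysis that isolates the resulting exclusions. Near the margin, one to a few entries can change the PP half of the rule in either direction; away from it they cannot. The overall non-inferiority claim keeps a false-positive rate of at most about 2.4% in the case examined, because ITT must also pass. The fragility figures rest on the assumed PP size, the assumed IV iron rate, an unadjusted interval and exclusions that all fall on one arm and one outcome. The number of off-database deviations is unknown. Nothing here shows that any exclusion was made in view of its effect.

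**What to change.** In addendum section 8:

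1. Accept a spreadsheet entry only if it meets a rule written in v3.0 section 8.4 or addendum section 8, or if dated minutes show that it was decided before the original lock. Record its date, source and rule in the deviation dataset before the post hoc efficacy programs are run.
2. Do not use the case-by-case category for decisions first made after CSR v1.0.
3. Repeat post hoc Table 14.2.2.2 with all spreadsheet-only exclusions restored, as a sensitivity analysis. State in version 2 of the CSR whether the PP conclusion depends on them. This should not be a further pass/fail condition, because the restored subjects are by definition judged to have major deviations.

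The cost is a few sentences, some dataset entries and one more run of an existing table. The PP statement may turn out less favourable.
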